1.2 Secondary Objectives

- 1.2.1 To observe and record anti-tumor activity. Although the clinical benefit of pinometostat has not been fully established, the intent of offering this treatment is to provide a possible therapeutic benefit, and thus the patient will be carefully monitored for tumor response and symptom relief in addition to safety and tolerability
- 1.2.2 Estimate biologic activity of 7 day window treatment of pinometostat monotherapy
- 1.2.3 Estimate the toxicity profile of pinometostat alone (week 1) and in combination with daunorubicin and cytarabine
- 1.2.4 Estimate event free and overall survival of patients with MLL rearranged acute myeloid leukemia after combination treatment with pinometostat, daunorubicin, and cytarabine
- 1.2.5 Estimate the early death rate (death \leq 30 days) of pinometostat, daunorubicin, and cytarabine
- 1.2.6 Determine the rate of MRD negativity by clinical flow cytometry on post-treatment recovery bone marrow

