6.6 Duration of Follow Up

Patients will be followed until the earliest of progressive disease, allogeneic stem-cell transplant, other investigational anti-leukemia therapy including cell therapy given while in remission, or lost to follow-up which will lead to removal from the study, or until death, whichever occurs first. Patients removed from study for unacceptable adverse event(s) will be followed until resolution or stabilization of the adverse event.

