Length of study treatments

Study treatment will end after either 35 days (first induction) or 28 days (with calendar reset to day 1 on the first day of 5+2 in second induction attempt) of pinometostat. Patients should then receive standard of care consolidative therapy including allogeneic bone marrow transplant, but these are not considered study treatments. No specific consolidation is mandated.

Follow-up period

Patients will be followed until the soonest of death, alternative leukemia therapy (i.e. for relapsed or refractory disease; this is excluding the planned consolidation that may directly follow the study treatment) initiated, enrollment on another therapeutic clinical trial, bone marrow transplantation, voluntary or involuntary withdrawal from study (see section 6.5) or lost to follow-up.

Toxicity assessment

All patients who receive any amount of the study drug will be evaluable for toxicity. Toxicity will be graded and reported according to the Common Terminology Criteria for Adverse Events (CTCAE) Version 5. The CTEP Active Version of the CTCAE is identified and located on the CTEP website at http://ctep.cancer.gov/protocolDevelopment/electronic_applications/ctc.htm. All appropriate treatment areas should have access to a copy of the CTEP Active Version of CTCAE.

It is recognized that drug-related toxicity in this population may be difficult to ascertain, given the aggressive hematologic disease. Investigators will attempt to assign attribution of toxicities to each drug if possible. Toxicity attributed to any of the three agents will be considered dose limiting. Dose limiting toxicity will be divided into non-hematologic and hematologic toxicity.

Dose-limiting toxicity

Definitions of dose-limiting toxicities are in section 6.2.

Patients who receive at least 1 dose of pinometostat during cycle 1 will be considered to be evaluable for toxicity/DLT and will not be replaced during the dose escalation phase of the trial unless the PI determines that further additional patients at that dose level are required for safety purposes; the context in which DLTs are noted (before or after the introduction of 7+3) will be considered in this decision. Patients with transient liver function test abnormalities (AST, ALT, bilirubin, or alkaline phosphatase) that resolve to < grade 1 within 5 days will not be considered DLT. Infection will not constitute DLT unless it is felt that the infection resulted from

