9.3 Analysis of Secondary Endpoints

Secondary endpoints we are evaluating are:

- Toxicity frequencies for each patient, according to CTCAE v5
- Time to hematologic count recovery will be analyzed using lab evaluation of complete blood counts and differential
- Differential blast counts between screening and day 8 will be analyzed using lab evaluation of complete blood counts and differential
- Rate of MRD positivity will be evaluated by multiparameter flow cytometry, next-generation sequencing (or both) after induction therapy among those patients who attain morphologic and cytogenetic CR
- Progression free survival for all patients, defined as the time from the start of study treatment until progression or death, whichever occurs earliest. Patients will be censored at earliest of loss to follow-up, allogeneic stem-cell transplantation, or initiation of other anti-leukemia therapy when in remission
- Overall survival for all patients

Every report will contain all patients included in the study. For the response calculation, the report will contain at least a section with all eligible patients. Another section of the report may detail the response rate for evaluable patients only. The maximum grade for each type of toxicity will be recorded for each patient, and frequency tables will be reviewed to determine toxicity patterns. CR rate and Rate of MRD positivity will be calculated with the exact binomial 95% confidence intervals. The Kaplan-Meier method will be used to estimate time to progression and overall survival.

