11. STUDY CALENDAR

Baseline evaluations are to be conducted within 1 week prior to start of protocol therapy. In the event that the patient's condition is deteriorating, laboratory evaluations should be repeated in order to decide if therapy should be continued.

Table 11.1: Initial treatment plan.

| | Pre-Study / Screening | Wk 1 | Wk 2 | Wk 3 | Wk 4 | Wk 5 | Off Study ^c | Long Term Follow-Up ^f |
|---|-----------------------|------|----------------|------|------|----------------|------------------------|----------------------------------|
| Pinometostat | | A | A | A | A | A | | |
| Cytarabine | | | B | | | | | |
| Daunorubicin | | | C | | | | | |
| Informed consent | X | | | | | | | |
| Demographics | X | | | | | | | |
| Medical history | X | | | | | | | |
| Concurrent meds | X | X | X | X | X | X | | |
| Physical exam | X | X | X | X | X | X | X | |
| Vital signs | X | X | X | X | X | X | X | |
| Height and Weight | X | X | X | X | X | X | X | |
| Performance status | X | | | | | | | |
| CBC w/diff, plts, PT/INR, aPTT | X | X | X | X | X | X | X | |
| Serum chemistry ^a | X | X | X | X | X | X | X | |
| EKG (as indicated) | X | | | | | | | |
| Echocardiogram/MUGA | X | | | | | | | |
| Adverse event evaluation | | X | X | X | X | X | | |
| B-HCG | X ^b | | | | | | | |
| Bone marrow aspiration and biopsy | X | | X | | X | X ^d | | |
| Bone marrow metaphase karyotype | X | | X | | X | X ^d | | |
| Bone marrow MLL (KMT2A) translocation by FISH | X | | X | | X | X ^d | | |
| Immunophenotyping (BM and PB) | X | | X | | | X ^d | | |
| Differentiation analysis | X | | X ^e | | | X ^d | | |
| Comprehensive mutational profile | X | | X ^e | | | X ^d | X | |
| Survival | | | | | | | | X ^f |

A: Pinometostat: Dose as assigned; weeks 1-5, days 1-35
B: Cytarabine: 100 mg/m² continuous IV infusion; week 2, days 8-14
C: Daunorubicin: 60 mg/m² IV; daily days 8-10 of week 2
a Albumin, alkaline phosphatase, total bilirubin, bicarbonate, BUN, calcium, chloride, creatinine, glucose, uric acid, LDH, phosphorus, potassium, total protein, SGOT [AST], SGPT [ALT], sodium.
b. Serum or urine pregnancy test (women of childbearing potential).
c. Off-study evaluation.
d. And at count recovery in week 5 or beyond
e. Day 8 of week 2, and at relapse (if applicable)

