f. Long-term follow-up for survival should be conducted at least monthly after patient has completed treatment and should include reporting of survival, subsequent therapy, transplant (if performed). This should be done in person if patient is being followed clinically at the treating center, or by telephone otherwise. After 1 year, this can be done every 3 months. After 5 years, further follow-up is not required.

Table 11.2: Treatment plan for re-induction.

| | Wk 1 | Wk 2 | Wk 3 | Wk 4 | Off Study ^c | Long Term Follow-Up ^g |
|---|----------------|----------------|---------|----------------|------------------------|-------------------------------------|
| Pinometostat | A | A | A | A | | |
| Cytarabine | B | | | | | |
| Daunorubicin | C | | | | | |
| Concurrent meds | X | X | X | X | | |
| Physical exam | X | X | X | X | X | |
| Vital signs | X | X | X | X | X | |
| Height and Weight | X | X | X | X | X | |
| Performance status | X | X | X | X | X | |
| CBC w/diff, plts, PT/INR, aPTT | X | X | X | X | X | |
| Serum chemistry ^a | X | X | X | X | X | |
| Echocardiogram/MUGA ^f | X ^f | | | | | |
| Adverse event evaluation | X | X | X | X | | |
| Bone marrow aspiration and biopsy | | X | | X ^d | | |
| Bone marrow metaphase karyotype | | X | | X ^d | | |
| Bone marrow MLL (KMT2A) translocation by FISH | | X | | X ^d | | |
| Immunophenotyping (BM and PB) | | X | | X ^d | | |
| Differentiation analysis | | X ^e | | X ^d | | |
| Comprehensive mutational profile | | X ^e | | X ^d | X | |
| Survival | | | | | | X ^g |

A: Pinometostat: Dose as assigned; weeks 1-4, days 1-28 of a “reset” calendar where day 1 is the start of 5+2 reinduction
 B: Cytarabine: 100 mg/m2 continuous IV infusion; days 1-5 of re-induction
 C: Daunorubicin: 60 mg/m2 IV; daily days 1,2 of re-induction
 a Albumin, alkaline phosphatase, total bilirubin, bicarbonate, BUN, calcium, chloride, creatinine, glucose, uric acid, LDH, phosphorus, potassium, total protein, SGOT [AST], SGPT [ALT], sodium.
 b. Serum pregnancy test (women of childbearing potential).
 c. Off-study evaluation.
 d. At count recovery in week 4 or beyond
 e. Day 8 of week 2, and at relapse (if applicable), and off-study
 f. Echocardiogram or MUGA should demonstrate EF ≥45% before the second induction cycle (“re-induction”) is initiated

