 g. Long-term follow-up for survival should be conducted at least monthly after patient has completed treatment and should include reporting of survival, subsequent therapy, transplant (if performed). This should be done in person if patient is being followed clinically at the treating center, or by telephone otherwise. After 1 year, this can be done every 3 months. After 5 years, further follow-up is not required.

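### Sections 6.6 and 9.1 end follow-up before most deaths while the calendar requires survival contacts to 5 years, with no rule on which governs overall survival; the event-free survival objective has no matching analysis in 9.3

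*Combined protocol and SAP*

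**What the plan says.** **Follow-up.** Three places set its length.

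- Section 6.6: "Patients will be followed until the earliest of progressive disease, allogeneic stem-cell transplant", other investigational anti-leukemia therapy given in remission, or loss to follow-up. These take the patient off study. Death is the remaining end point, whichever comes first.
- Section 9.1, follow-up period: "Patients will be followed until the soonest of death, alternative leukemia therapy" for relapsed or refractory disease, another therapeutic trial, transplant, withdrawal or loss to follow-up. Progression is not itself on this list.
- Section 11: Tables 11.1 and 11.2 have a separate column headed "Long Term Follow-Up" whose only entry is survival. Footnotes f and g say "Long-term follow-up for survival should be conducted at least monthly after patient has completed treatment", then every 3 months after year 1, ending at 5 years. The contacts also record subsequent therapy and transplant.

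**Endpoints.** Objective 1.2.4 is to "Estimate event free and overall survival of patients with MLL rearranged acute myeloid leukemia". Section 9.3 lists "Progression free survival for all patients, defined as the time from the start of study treatment until progression or death, whichever occurs earliest", censored at loss to follow-up, transplant, or other anti-leukemia therapy started in remission. It lists OS for all patients without a time origin or censoring rule, and adds: "The Kaplan-Meier method will be used to estimate time to progression and overall survival". Section 9 does not mention EFS.

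**Disease status.** Section 12.1 defines progressive disease and primary refractory disease as separate categories. Section 12.2 defines hematologic relapse, with 5% marrow blasts as one sufficient criterion.

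**The concern.** Two separate defects affect the survival analyses.

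**OS.** The events that end follow-up in 6.6 and 9.1 are the ordinary course of this disease. Sections 2.4 and 9.1 describe transplant as standard consolidation, and salvage is the natural sequel to induction failure or relapse. Most deaths would come after one of these events. A site that reads 6.6 or 9.1 literally stops contact there, and the Kaplan-Meier estimate treats patients at high risk of death as if they were censored at random. Contacts not made at the time cannot always be recovered.

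**EFS.** The objective has no analysis. PFS does not stand in for it, because the plan never says that failure to reach remission, or relapse after remission, is a progression event. Two analysts could draw different curves from the same data, and the PFS curve could lie well above EFS.

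**Working it through.** **1. The plan's own figures.** The plan states no survival rate, event count or precision for OS, PFS or EFS, so there is nothing to reproduce on this point. The primary design does reproduce. Summing P(Bin(13,p) = x) × P(Bin(18,p) ≥ 24 − x) over x = 9 to 13 gives 0.0951 at p = 0.65 (stated 0.0951) and 0.9036 at p = 0.85 (stated 90%). It uses CR/CRi only and is untouched.

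**2. The follow-up rules side by side.**

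| Event | 6.6 | 9.1 | Footnotes f, g |
|---|---|---|---|
| Progressive disease | stop | not listed | continue |
| Salvage for relapsed or refractory disease | not listed | stop | continue, recorded |
| Transplant | stop | stop | continue, recorded |
| Other investigational therapy in remission | stop | stop if on another therapeutic trial | continue, recorded |
| Latest end | death | death | 5 years |

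Sections 6.6 and 9.1 therefore also differ from each other. No text ranks the three.

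**3. Is PFS the same as EFS?** Take one limb of progressive disease in 12.1: a rise of more than 50% in marrow blasts over baseline, and at least 15 points if baseline is below 30%. Suppose baseline means pre-treatment, which 12.1 does not state.

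- Baseline 20% (the diagnostic floor in 5.2.2): max(1.5 × 20, 20 + 15) = 35%.
- Baseline 40%: more than 1.5 × 40 = 60%.
- Baseline above 66.7%: more than 1.5 × 66.7 = 100%, which is impossible.

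Other limbs exist (persistent marrow blasts above 70%, rising peripheral blasts, new extramedullary disease), but a marrow relapse at 5% blasts need not meet any of them. Section 9.3's reference to therapy in remission hints that loss of remission counts as progression, without saying so. Section 9.4.2 uses disease progression in yet another sense, for response categories 4 to 9.

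**4. Size, as an illustration.** Monte Carlo, 400,000 patients in each of 24 scenarios (2 × 2 × 2 × 3), read at 12 months. Only the CR/CRi rates come from the protocol (H0 and Ha); every other input is assumed.

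- CR/CRi 65% with early death 8%, or 85% with early death 5%; the rest refractory. Early death uniform over month 0 to 1; CR or refractory result dated month 2.
- Relapse from CR exponential, median 9 or 14 months. Survival after relapse or refractory result exponential, median 4 or 6 months. No death in remission without transplant.
- Transplant: none; or planned in 50% of CR patients at a uniform time in months 3 to 6, given only if not yet relapsed, halving the relapse hazard, with non-relapse mortality of 10% or 25% at 12 months after transplant.
- 6.6 run: stop at transplant, or at relapse or refractory result in the share counted as 12.1 progression.
- 9.1 run: stop at transplant, or at salvage 0.5 month after relapse or refractory result in the share starting it.
- EFS event: relapse, refractory result or death. PFS: the same, except that cases not counted as progression have their event at death. Both censored at transplant.

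True 12-month OS is 0.486 to 0.737 and EFS 0.300 to 0.520.

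| Rule followed | Share | Bias in Kaplan-Meier OS |
|---|---|---|
| 6.6 | 30% count as progression | -0.010 to +0.071 |
| 6.6 | 70% | +0.105 to +0.222 |
| 6.6 | 100% | +0.212 to +0.434 |
| 9.1 | 70% start salvage | +0.089 to +0.188 |
| 9.1 | 100% | +0.182 to +0.357 |
| Calendar | any | none |

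PFS minus EFS is 0 if all such cases count as progression, +0.023 to +0.084 if 70% do, and +0.058 to +0.198 if 30% do.

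Check: under 6.6 with 100% counted, only early deaths are seen, so Kaplan-Meier OS must equal 1 − 0.08 = 0.92 or 1 − 0.05 = 0.95. The runs gave 0.919 to 0.951.

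Scale: the 95% half-width with 31 patients, 1.96 × √(p(1 − p)/31), is 0.176 at p = 0.50 and 0.154 at p = 0.74.

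**The case against.** The best defence concerns OS. The calendar puts an off-study visit before a separate survival column, and its footnotes record subsequent therapy and transplant, which makes sense only if contact continues past those events. On that reading 6.6 and 9.1 govern disease follow-up, the calendar governs survival, and no bias arises. The reading is plausible and probably intended. But no text states it, neither 6.6 nor 9.1 limits itself to disease follow-up, and 6.6 takes patients off study at its events. A clarification is still needed.

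The second objection is that the simulated sizes rest on assumptions. That stands. The range under 6.6 is driven mainly by the assumed share meeting 12.1 progression, and its top band follows mechanically from seeing early deaths only. The bias is not always upward: a few scenarios with 30% counted, all with transplant at the lower non-relapse mortality, gave slightly negative values. The runs also leave out two named stops, investigational therapy in remission and enrolment on another trial. The figures show direction and possible scale and are not estimates for this trial.

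Third, the blast arithmetic covers one limb of 12.1 and one reading of baseline. That is correct, but the EFS point does not depend on it: the objective names EFS and 9.3 never does. Nothing on the other side answers that.

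**Conclusion.** Both parts hold, and the plan is wrong as written.

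- **EFS:** a stated secondary objective has no defined endpoint or analysis, and PFS as written need not estimate it. On the assumed inputs the gap at 12 months is 0 to 20 points, set by what counts as progression.
- **OS:** the follow-up rules conflict. If the calendar governs, there is no bias. If 6.6 or 9.1 is followed literally, OS is generally overstated; in the less favourable scenarios the bias matches or exceeds the sampling half-width of about 15 to 18 points.

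The textual findings rest on the documents alone; the sizes rest on the assumptions listed. These are secondary, estimation-only endpoints and the primary CR/CRi test is unaffected, so this should be fixed but does not threaten the main conclusion.

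**What to change.** 1. **Sections 6.6 and 9.1:** reconcile the two lists, and state that progression, transplant and new therapy end on-study disease follow-up but not the survival contacts in footnotes f and g.
2. **Section 9.3, OS:** define it as day 1 to death from any cause, censored at last contact.
3. **Section 9.3, EFS:** replace PFS with EFS, or add EFS. Define it as day 1 to the first of failure to reach CR/CRi after the last induction (with a stated event date, for example that of the marrow showing it), hematologic relapse as in 12.2, or death, keeping the existing censoring at transplant. Report EFS without that censoring only if relapse status is collected after transplant.
4. **If PFS is kept:** state which categories in 12.1 and 12.2 count as progression, and use one name throughout in place of both PFS and time to progression.

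**Cost.** Wording in three sections. The survival contacts are already scheduled. Section 12 already asks for re-evaluation at least every four weeks after discharge, which largely supports EFS censored at transplant, though that schedule depends on clinical context and has no stated end. EFS without transplant censoring would need one added item, relapse status and date, at the existing contacts.

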7. DOSING DELAYS/DOSE MODIFICATIONS

No intra-patient adjustment of chemotherapy doses is permitted. No intra-patient escalation of study drug is permitted, except as outlined below and with permission of principal investigator. Dose reduction of pinometostat should occur for grade 3 toxicities possibly related to this agent,

excluding hematologic toxicities and select other toxicities that can occur in the phase 2 expansion portion of the study. These select other toxicities for which a dose adjustment is not required include nausea, vomiting, or diarrhea that is manageable without parenteral or enteral feeding; electrolyte abnormalities that are correctable within 48 hours; and grade 3 infections which are expected in this population.

Daunorubicin and cytarabine are only rarely held during the seven-day intensive induction therapy for AML. Dose modifications to daunorubicin or cytarabine are not recommended for treatment-emergent adverse events, and should be discussed with the principal investigator. For patients with a total bilirubin between 1 and 1.5xULN, the daunorubicin dose may be decreased by 75% after discussion with the principal investigator.

| Event | Management/Next Dose for Pinometostat |
|---------------------|--|
| ≤ Grade 1 | Full dose |
| Grade 2 | Full dose |
| Grade 3 | Hold until recovery of < grade 3, then re-initiate with a one-third dose reduction. For example, if the dose was 90 mg/m ² /day, re-initiate at 60 mg/m ² /day. If the dose was 60 mg/m ² /day, re-initiate at 40 mg/m ² /day. If toxicity reoccurs, therapy should be discontinued. See exceptions in section 6, Dose Limiting Toxicities |
| Grade 4 | Discontinue therapy permanently. |

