2.3 Cytarabine and Daunorubicin

Patients will be treated with the standard of care for AML with 7 days of Cytarabine 100 mg/m²

by continuous intravenous infusion and 3 days of Daunorubicin 60 mg/m² daily (“7+3”). This is a standard of care AML remission induction regimen for younger, fit patients.¹⁷⁻¹⁹ This combination of medications has been the most successful induction regimen for AML to date.¹⁸ Per NCCN guidelines, the dose of Cytarabine should be 100 mg/m², as stated above, and the dose of daunorubicin should be 60-90 mg/m². Daunorubicin will be dosed at 60 mg/m² in this study. These doses will stay constant and not be escalated in our study, as is standard of care. Common side effects of cytarabine include increased risk for blood clots, rash, diarrhea, anorexia, nausea and vomiting, mouth sores, and anemia. Common side effects of daunorubicin are nausea, vomiting, and hair loss. These side effects will be treated with supportive care, transfusions, and further treated medically as needed.

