3. PATIENT SELECTION

3.1 Eligibility Criteria

- 3.1.1 Patients must have histologically confirmed Acute Myeloid Leukemia by World Health Organization (WHO) criteria. Patients with treatment-related acute leukemia are eligible if they do not exceed lifetime anthracycline doses as outlined below.
- 3.1.2 Presence of a cytogenetic rearrangement of *KMT2A* (MLL) by interphase Fluorescent *in-situ* Hybridization (FISH).
- 3.1.3 Patients must have previously untreated (with exception of hydroxyurea for count control, or ATRA for acute promyelocytic leukemia (APML) that was initially suspected but later ruled out) AML by World Health Organization (WHO) criteria. Treatment with hydroxyurea for count-control of hyperproliferative disease is permitted before and during treatment with pinometostat and chemotherapy.
- 3.1.4 Age ≥ 14 years at time of screening, although individual sites may further restrict age eligibility in accordance with local IRB and hospital policy.
- 3.1.5 ECOG performance status ≤ 2 (Karnofsky $\geq 60\%$; see Appendix A).
- 3.1.6 Patients must have adequate organ function at the time of eligibility screening as defined below:
- Total bilirubin $\leq 1.5 \times$ institutional ULN, unless elevated due to Gilbert syndrome, hemolysis, or leukemia
 - AST(SGOT)/ALT(SGPT) $\leq 2.5 \times$ institutional ULN, unless due to leukemia in which case $< 5 \times$ ULN
 - Creatinine $\leq 1.5 \times$ institutional ULN
OR
 - Glomerular filtration rate (GFR) ≥ 60 mL/min/1.73 m² for patients with creatinine levels above institutional normal.
 - Coagulation: PT and aPTT $\leq 1.5 \times$ ULN (both)

 - Human immunodeficiency virus (HIV)-infected patients on effective antiretroviral therapy with undetectable viral load within 6 months are eligible for this trial.
 - If evidence of chronic hepatitis B virus (HBV) infection, HBV viral load must be undetectable on suppressive therapy if indicated.
 - If history of hepatitis C virus (HCV) infection, must be treated with undetectable HCV viral load.

- For pediatric patients, a serum creatinine based on age/gender as follows:

| Age | Maximum Serum Creatinine (mg/dL) | |
|------------------|----------------------------------|--------|
| | Male | Female |
| 10 to < 13 years | 1.2 | 1.2 |
| 13 to < 16 years | 1.5 | 1.4 |
| ≥ 16 years | 1.7 | 1.4 |

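### Section 7 bars intra-patient chemotherapy adjustment, then allows a 75% daunorubicin decrease at bilirubin values that are eligible at entry; the passages need one rule

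*Combined protocol and SAP*

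**What the plan says.** Section 7 makes three statements about the chemotherapy backbone.

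- It opens with a bar: "No intra-patient adjustment of chemotherapy doses is permitted". The carve-out for what is outlined later belongs to the next sentence, which concerns escalation of pinometostat.
- Its second paragraph is softer: "Dose modifications to daunorubicin or cytarabine are not recommended for treatment-emergent adverse events, and should be discussed with the principal investigator".
- It then makes an allowance. "For patients with a total bilirubin between 1 and 1.5xULN", "the daunorubicin dose may be decreased by 75% after discussion with the principal investigator". It does not say whether the value is the one at screening, the one on the day of daunorubicin, or any value during induction.

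Other sections bear on the same dose.

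- Section 2.3 states "Daunorubicin will be dosed at 60 mg/m² in this study" and adds "These doses will stay constant and not be escalated in our study".
- Section 3.1.6 admits patients with total bilirubin up to 1.5 × ULN. Its exception, "unless elevated due to Gilbert syndrome, hemolysis, or leukemia", covers values above that limit.
- Section 6.1.3 gives daunorubicin in re-induction as 60 mg/m² on two days.
- Section 9.1 says re-induction uses both drugs at the doses given in the initial induction.
- Section 9.4.2 keeps all eligible patients in the main response analysis, including those whose drug administration was incorrect, and does not let subanalyses support efficacy conclusions.

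**The concern.** A site with a patient in the bilirubin band finds a prohibition, a discouragement and a permission in one section, with no statement of which governs. Different sites could reasonably act differently on the same patient. Because the allowance is large, the resulting doses would be far apart.

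The backbone matters to the analysis. Section 9.1 sets the remission rate against historical controls, and Section 2.4 describes those controls as treated with 7+3 and, if needed, 5+2. Section 9.1 also counts toxicity attributed to any of the three agents as dose limiting. If delivered daunorubicin varies with the reading of Section 7, both the remission rate and the toxicity counts become harder to interpret. It is also a matter of patient safety that a dosing instruction can be read in one way only.

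**Working it through.** **1. The plan's own design figures.** Section 9.1 gives n1 = 13 (stop at 8 or fewer responses), N = 31 (success at 24 or more), null rate 0.65 and alternative 0.85. With X1 ~ Bin(13, p) and X2 ~ Bin(18, p),

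P(success) = Σ over x = 9 to 13 of P(X1 = x) × P(X2 ≥ 24 − x).

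At p = 0.65 this is 0.0951, as stated. At p = 0.85 it is 0.9036, against the stated 90%. The design is correctly computed.

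**2. Does the trigger band overlap with eligibility?** The band in Section 7 is 1 to 1.5 × ULN. The entry limit in Section 3.1.6 is at most 1.5 × ULN. Every value in the band is therefore eligible without using any exception. The band can also be reached after entry: Section 10.1.1.1 lists increased blood bilirubin as possibly related to pinometostat, and Section 6.1.1 gives pinometostat on days 1–7, before daunorubicin starts on day 8. The missing time point therefore has practical consequences. Section 7 is also silent on patients admitted above 1.5 × ULN under the exception.

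**3. Dose under each sentence.** Planned daunorubicin is 60 mg/m² daily for three days.

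- Following the bar: 60 mg/m² per dose, 3 × 60 = 180 mg/m² in total.
- Following the allowance literally: 60 × (1 − 0.75) = 15 mg/m² per dose, 3 × 15 = 45 mg/m² in total.
- Ratio: 60/15 = 180/45 = 4.

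**4. Re-induction after a reduced first induction.**

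- Section 6.1.3: 2 × 60 = 120 mg/m².
- Section 9.1, carrying forward the dose used in the initial induction: 2 × 15 = 30 mg/m².

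The two instructions agree only if the first induction was not reduced.

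**5. Direction of any effect on the test.** The documents give neither the share of patients reduced nor any effect on remission. Purely as an assumption, let a share f be reduced and let their remission probability fall by d, so that the overall rate becomes p − f × d. Putting this into the formula in step 1 gives:

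| f | d | rate from 0.85 | P(success) | rate from 0.65 | P(success) |
|---|---|---|---|---|---|
| 0.10 | 0.10 | 0.84 | 0.873 | 0.64 | 0.077 |
| 0.20 | 0.20 | 0.81 | 0.756 | 0.61 | 0.039 |
| 0.30 | 0.30 | 0.76 | 0.505 | 0.56 | 0.011 |

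Under these assumptions power falls, and so does the chance of a false positive. The table shows direction only; it does not estimate what would happen in this trial.

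**The case against.** **Section 7 can be read as coherent.** On this view it states a general rule, then discouragement, then one optional exception that needs discussion with the principal investigator. The bar is also on intra-patient adjustment, not on every adjustment. If a baseline bilirubin value set the first dose, that would not clearly be a change within a patient. This much stands: the conflict inside Section 7 depends partly on when bilirubin is assessed. But the text does not say that the allowance is an exception or that it applies only at baseline, and a baseline-only reading would still sit against the fixed 60 mg/m² in Section 2.3.

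**Section 2.3 may mean only that chemotherapy is not escalated alongside pinometostat.** That is a fair reading of the sentence, so it is supporting evidence and not the core of the point.

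**Three stronger readings are tempting but unsupported.**

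- A reader might suspect that a decrease to 75% was meant. The text says by, and no other passage suggests otherwise.
- A reader might infer that the comparison with historical controls, the 24-of-31 rule or the toxicity counts is biased. The documents do not give the dosing rules of the historical series, the number of patients affected, or the effect of a reduction on remission or toxicity. No bias is shown, and an inflated type I error would not follow from a loss of response.
- A reader might infer that reductions would go unnoticed. Section 7 calls for discussion with the principal investigator, and Section 13.3 provides for minuted teleconferences every two weeks. What is missing is narrower: the analysis sections do not specifically ask for a listing of reduced-dose patients.

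**Conclusion.** The inconsistency is real and should be corrected. Within Section 7 a bar, a discouragement and a permission are not reconciled. The permission applies across a bilirubin band that is wholly eligible at entry, and it carries no time point. Taken literally, the choice of sentence moves daunorubicin between 60 and 15 mg/m² per dose (180 and 45 mg/m² over three days), and the re-induction instructions in Sections 6.1.3 and 9.1 then diverge as well.

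The size stated here is a difference in possible dose, resting on the literal wording. It is not an effect on the trial's result. The reduction is optional and may never be used, and its consequences for remission or dose-limiting toxicity cannot be derived from the documents. This is a wording inconsistency with safety and interpretive relevance, not an error in the statistical design.

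**What to change.** The sponsor should reconcile Sections 2.3, 3.1.6, 6.1.3, 7 and 9.1 into one unambiguous rule. It should state whether any daunorubicin reduction is allowed, its size, when the bilirubin value is assessed, and which dose applies in re-induction if the first induction was reduced. The investigators decide the clinical content; no dose or threshold is proposed here.

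Optionally, Section 9.4.2 could add a listing of delivered daunorubicin dose per patient and a descriptive remission rate (CR/CRi) by full versus reduced dose. All eligible patients should stay in the primary analysis, as that section already requires.

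The cost is a wording amendment and, if the option is taken, one descriptive output. The sample size, decision rule and error rates do not change.
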